5 STUDY POPULATION

5.1 Inclusion criteria

Participants are eligible to be included in the study only if all of the following criteria apply:

Age

1. Participant must be ≥ 18 years of age at the time of signing the informed consent.

Type of participant and disease characteristics

- 2a. Participant was eligible for MG0003 or MGC003 at the time of enrollment into either study and the participant either completed the Observation Period of MG0003 or MGC003 or required rescue therapy during the Observation Period of the lead-in studies.

Weight

- 3a. Body weight ≥ 35 kg at Visit 1.

Sex

4. Participants may be male or female.
 - A male participant must agree to use contraception as detailed in Appendix 4 (Section 10.4) of this protocol during the Treatment Period and for at least 90 days after the last dose of study treatment and refrain from donating sperm during this period.
 - Female study participants of childbearing potential must agree to use a highly effective method of birth control during the study and for a period of at least 90 days after their final dose of study medication. According to the International Council for Harmonisation (ICH) M3 (R2), highly effective forms of birth control are methods that achieve a failure rate of less than 1% per year when used consistently and correctly.
 - A female participant is eligible to participate if she is not pregnant (see Appendix 4, Section 10.4), not breastfeeding, and at least one of the following conditions applies:
 - Not a woman of childbearing potential (WOCBP) as defined in Appendix 4 (Section 10.4)
OR
 - A WOCBP who agrees to follow the contraceptive guidance in Appendix 4 (Section 10.4) during the Treatment Period and for at least 90 days after the last dose of study treatment.

Informed consent

5. Capable of giving signed informed consent as described in Appendix 1 (Section 10.1) which includes compliance with the requirements and restrictions listed in the informed consent form (ICF) and in this protocol.

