3.3 Definition of Baseline values

If not otherwise stated, Baseline values will be the last available value prior to or on the same date (and same time if time is collected for the individual assessment) of first administration of IMP in MG0004. Scheduled or unscheduled measurements can be used as the Baseline value.

Baseline values for serum or plasma complements and serum cytokines will be the Baseline values determined in MG0003.

Baseline for anti-drug antibody (ADA) for MG0004 should be the last measurement prior to receiving the very first rozanolixizumab (RLZ) infusion across all MG studies. Specifically, baseline for ADA is define as:

- MG0003 ADA baseline if participants randomized to RLZ groups in MG0003;
- MG0004 ADA baseline if participants randomized to placebo in MG0003.

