10.2.2 MG-specific autoantibodies

MG-specific autoantibodies (anti-MuSK/anti-AChR) will be summarized by first dose received and RLZ total at scheduled visits for observed values, absolute and percentage changes from Baseline. The maximum change from Baseline in MG-specific autoantibodies (absolute and percentage change) will be reported in the listing and summarized for each treatment.

MG-specific autoantibodies will also be summarized at scheduled visit by the participants who are anti-MuSK or anti-AChR autoantibody-positive at the Baseline visit.

Mean absolute and mean percentage change from Baseline values in MG-Specific autoantibodies will be plotted over time by treatment group and RLZ total. Additionally, mean percentage change from Baseline in anti-MuSK, total IgG, MG-ADL, QMG, and MG-C will be plotted by first dose received. The same plot will be repeated for percentage change from Baseline values in anti-AChR.

MG-specific autoantibodies will be listed, together with total IgG, MG-ADL, QMG, MG-C change from Baseline.

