13 APPENDICES

13.1 Quantitative Myasthenia Gravis scale

The QMG scale comprises 13 items, including ocular and facial movement, swallowing, speech, limb strength and forced vital capacity. Scoring for each item ranges from no weakness (0) to severe weakness (3), with an overall score range from 0 to 39, ie, a higher score indicates more severe disease. A 3-point change in the overall score is considered to be clinically relevant.

The QMG testing form is provided in [Table 13–1](#). The total score is obtained by summing the responses to each individual item.

[REDACTED]
[REDACTED] The score ranges from 0 to 33.

In the event of missing data, the following rules will be applied:

[figure not shown]
- If 1 or 2 items are not answered, the overall score will be obtained by imputing the missing items with the average score across the remaining items at the specific visit. The imputed value will be rounded to one decimal place
- If more than 2 items are missing the overall score will not be calculated at the specific visit

Table 13–1: Quantitative myasthenia gravis testing form

Item	None	Mild	Moderate	Severe
Grade	0	1	2	3

[REDACTED]

Item	None	Mild	Moderate	Severe
Grade	0	1	2	3

F=female; M=male.

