13.2 Myasthenia Gravis-Composite scale

The MG-C score items and associated scores are provided in [Table 13–2](#).

The MG-C score comprises 10 items, each of which is weighted differently in the calculation of the overall score. The overall score ranges from 0 to 50, with a higher score indicating more severe disease.

The total score is obtained by summing the responses to each individual item.

[figure not shown]

[figure not shown]
The score ranges from 0 to 41.

In the event of missing data at a particular visit, the MG-C score will not be calculated. Due to the different weighting applied to each item it is not possible to impute the missing data with the average score across the remaining items.

Table 13–2: MG-C score items and scoring algorithm

Item	Result/Grade	Result/Grade	Result/Grade	Result/Grade
------	--------------	--------------	--------------	--------------

^a Moderate weakness for head and neck items should be construed as weakness that equals roughly 50%+/-15% of expected normal strength. Any weakness milder than that would be mild and any weakness more severe than that would be classified as severe.

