13.3 Myasthenia Gravis-Activities of Daily Living

The MG-ADL score comprises 8 items, each with a score of 0 to 3. The total score is obtained by summing the responses to each individual item. Thus, the score ranges from 0 to 24 with a higher score indicating more disability. The MG-ADL testing form is provided in [Table 13-3](#). The total score is obtained by summing the responses to each individual item. Thus, the score ranges from 0 to 24.

In the event of missing data, the following rules will be applied:

- If 1 or 2 items are not answered, the overall score will be obtained by imputing the missing items with the average score across the remaining items at the specific visit. The imputed value will be rounded to one decimal place
- If more than 2 items are missing the overall score will not be calculated.

Table 13–3: MG-Activities of Daily Living

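### The SAP 10.2.2 figure plots MG-ADL, QMG and MG-C as mean percentage change, although Baseline can be 0 or close to it; absolute change is the safer scale

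*SAP*

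**What the plan says.** After the plots of the autoantibodies themselves, SAP 10.2.2 adds a combined display: "mean percentage change from Baseline in anti-MuSK, total IgG, MG-ADL, QMG, and MG-C will be plotted by first dose received". It continues: "The same plot will be repeated for percentage change from Baseline values in anti-AChR". Nothing there says what happens to a score's percentage change when Baseline is 0, or sets a smallest usable Baseline.

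The three scales all include 0:
- MG-ADL (SAP 13.3): "Thus, the score ranges from 0 to 24 with a higher score indicating more disability".
- QMG (SAP 13.1): "with an overall score range from 0 to 39, ie, a higher score indicates more severe disease".
- MG-C (SAP 13.2): "The overall score ranges from 0 to 50, with a higher score indicating more severe disease".

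The denominator is the MG0004 Baseline, not the value at lead-in entry. Under SAP 3.3, "Baseline values will be the last available value prior to or on the same date" as the first IMP administration in MG0004.

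The disease-related entry condition in Protocol 5.1 looks back to the lead-in study: "Participant was eligible for MG0003 or MGC003 at the time of enrollment into either study", provided that "the participant either completed the Observation Period of MG0003 or MGC003 or required rescue therapy during the Observation Period" of the lead-in. Neither Protocol 5.1 nor 5.2 sets a minimum MG-ADL, QMG or MG-C score at Visit 1. Exclusion criterion 7 removes participants with severe oropharyngeal or respiratory weakness, not those with mild disease.

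**The concern.** Percentage change suits a quantity that is well away from 0 at Baseline, such as total IgG. It suits a bounded severity score badly when some Baselines may be at or near the floor.

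Two distortions follow, and they pull in opposite directions. A participant at Baseline 0 has no percentage change. That participant cannot improve and may worsen, so the loss flatters the score line. The same participant still contributes to the total IgG line, so lines in one figure describe different people. A participant at Baseline 1 or 2 can fall by at most 100% but can rise by several hundred percent, so a few such participants can pull the mean towards worsening.

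At stake is the reading of one descriptive figure and its repeat, which set antibody lowering beside clinical response. The figure could disagree with the score tables in SAP 9.1.1 to 9.1.3, which use change in points.

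**Working it through.** The plan states no expected value for this figure, so there is nothing of its own to reproduce. The check compares the planned statistic, the mean over participants of 100 × (Y - B)/B, with the mean of (Y - B). B is the MG0004 Baseline score and Y the score at a later visit. The ranges come from SAP 13.1 to 13.3. The participant values below are assumptions chosen to show the mechanism.

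**1. Asymmetry.** On the 0 to 24 MG-ADL scale, Baseline 8 allows -100% to 100 × (24 - 8)/8 = +200%. Baseline 1 allows -100% to 100 × (24 - 1)/1 = +2300%.

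**2. Near-zero Baseline.** Nine participants go from 8 to 6 (-25% each) and one goes from 1 to 4 (+300%).
- Mean change: (9 × (-2) + 3)/10 = -1.5 points.
- Mean percentage change: (9 × (-25) + 300)/10 = +7.5%.
- For comparison, the percentage change in the group mean is (58 - 73)/73 = -20.5%, and the median percentage change is -25%.

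**3. Zero Baseline.** Let the tenth participant go from 0 to 4 instead.
- Mean change over all ten: (9 × (-2) + 4)/10 = -1.4 points.
- Mean percentage change: -25% on n = 9. The participant who worsened is not shown.

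**4. Order of dose groups.** Group A has nine going from 8 to 5 and one from 1 to 4; group B has ten going from 8 to 6.
- A: (9 × (-3) + 3)/10 = -2.4 points, and (9 × (-37.5) + 300)/10 = -3.75%.
- B: -2.0 points and -25%.

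A is better in points and looks much worse in percent.

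**5. Break-even share.** Suppose a share p starts at 1 and worsens by k points, and the rest go from 8 to 6. The mean percentage change is zero when 100k × p = 25 × (1 - p), so p = 25/(100k + 25).

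| k | p | Mean change at that p: kp - 2(1 - p) |
|---|---|---|
| 1 | 20.0% | -1.40 |
| 2 | 11.1% | -1.56 |
| 3 | 7.7% | -1.62 |
| 5 | 4.8% | -1.67 |

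**6. How often the sign could change.** This was simulated for MG-ADL, rounded and truncated to 0 to 24, with N = 120 (half of the maximum of 240 in SAP 3.9). With assumed Baseline means of 5 to 8 and SD 3.5, about 1.6 to 10% of participants have Baseline 0 and 4 to 14% have Baseline 1 or 2. With a between-visit correlation of 0.5 to 0.7, the chance that the mean percentage change is positive while the mean change in points is negative is:

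| True mean change | Chance of opposite signs |
|---|---|
| -0.5 | about 50 to 80% |
| -1 | about 8 to 46% |
| -2 | 0 to 1% |

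With a uniform shift and no regression to the mean (Baseline mean 4 to 8, SD 3 to 3.5), it is 0 to 6% for changes of -1 and -2.

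**The case against.** The case for leaving the figure alone has real content.

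- **The figure is supplementary.** A reader might infer that it is the plan's only link between antibody lowering and clinical response. It is not. SAP 10.2.2 also lists autoantibodies with total IgG and change in the three scores. SAP 10.3.2 pairs percentage change in IgG with change in MG-ADL in points, in a table, individual plots and a listing. The table and plots there are split by ADA category or limited to ADA-positive participants, so they do not replace this figure. They do show that the SAP already uses the proposed pairing.
- **Evidence for low Baselines is thin.** The Baseline MG-ADL category below 5 (SAP 4.9 and 6.2) might be read as a forecast of low scores. SAP 14.1 says the cutoff came from MG0003, and the category also contains scores of 3 and 4. Minimum symptom expression (SAP 9.2.8) concerns scores reached on therapy. Protocol 4.2 describes lead-in participants as having moderate to severe symptoms, and they enter after the Observation Period or because they need rescue. Low Baselines are permitted, not shown to be common.
- **QMG and MG-C.** For these two, the support is only that 0 lies on the scale.
- **One axis has a use.** Percent lets five measures in different units share a plot.

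These points limit the size of the concern. They do not supply the missing rule for a zero Baseline or remove the asymmetry. The SAP does address unusable Baselines elsewhere: SAP 10.4.4 repeats the anti-tetanus summary without participants whose Baseline titer is undetectable.

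**Conclusion.** The point stands as a minor one. As written, the figure drops any participant with a zero Baseline score and gives outsized weight to Baselines of 1 or 2, most plausibly for MG-ADL. It can therefore differ in size from the tables in SAP 9.1.1 to 9.1.3 and, when the mean change is small, possibly in sign.

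A reader might go further and infer that the figure will probably show the wrong direction. The documents do not support that. They give no Baseline distribution, so every frequency above rests on assumed means, SDs and correlations, and under those a change of sign is rare for mean improvements near 2 points. Nor are the efficacy results at risk: the score tables use points and SAP 9 plans no statistical testing.

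A related gap concerns the antibody lines. Protocol 4.2 requires anti-AChR or anti-MuSK antibodies, so a participant may have little or none of the one plotted. SAP 10.2.2 plans a separate summary for participants positive at Baseline but does not say that the figure is limited to them.

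**What to change.** In SAP 10.2.2, for the combined figure and its anti-AChR repeat:
- plot mean absolute change from Baseline for MG-ADL, QMG and MG-C, on a second axis or in separate panels;
- keep mean percentage change for total IgG, and for each autoantibody among participants positive for it at Baseline;
- show n per visit for every line.

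This puts the scores on the scale used for them in the rest of the SAP. It needs no new data and costs about a sentence of SAP text and a revised figure layout. The downside is that the five measures no longer share one axis. Because the score ranges end at 24, 39 and 50, separate panels may read better than one shared second axis.

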10.3 Anti-drug antibody and neutralizing antibody (NAb) status

For the immunogenicity assessment, two types of anti-drug antibody (ADA) assays will be performed, a binding anti-drug antibody assay and a neutralizing antibody assay.

For the binding assay, the ADA of rozanolixizumab will be measured using a three-tiered assay approach: screening assay, confirmatory assay and titration assay. Any sample confirmed positive for the binding ADA assay will be tested in the neutralizing assay, which produces a positive or negative result.

Evaluation of rozanolixizumab immunogenicity will be performed using data from all evaluable study participants in the SS, defined as all study participants who have an evaluable pretreatment (baseline) sample (negative or positive ADA sample status), and at least 1 evaluable post-baseline value.

Study participants with an evaluable pretreatment (baseline) sample but without a single evaluable sample taken post-baseline will be included in the reporting of pre-existing ADA but excluded from all other immunogenicity analyses.

10.3.1 Data consideration

ADA Sample Status

The ADA sample status will be determined for each pre-treatment (Baseline) and post-treatment (post-Baseline) visit where samples are taken for ADA analysis.

- Sample values that are either 'negative screen' or 'positive screen' and 'negative immunodepletion' will be defined as **ADA negative** if corresponding rozanolixizumab concentrations are equal or below the validated drug tolerance limit of the ADA assay (200µg/mL rozanolixizumab) allowing detection of 100ng/mL ADA
- Sample values that are either 'negative screen' or the combination of 'positive screen' and 'negative immuno-depletion', but with corresponding rozanolixizumab concentrations above the validated drug tolerance limit of the ADA assay, will be defined as **ADA inconclusive**
- Sample values that are 'positive screen' and 'positive immunodepletion' will be defined as **ADA positive**
- Samples that could not be tested for ADA status due to inadequate sample volume, mishandling, or errors in sample collection, processing, storage, etc., will be defined as **Missing**.

Note: if a participant has no baseline ADA, then she/he can't be treated as "Inconclusive".

Neutralizing antibody (NAb) sample status (positive/negative/missing) will be determined for ADA positive samples. Samples that are NAb positive will be evaluated in a titration assay to quantify the NAb level and will be reported as titer.

Definition of ADA Baseline

Baseline for ADA should be the last measurement prior to receiving the very first rozanolixizumab (RLZ) infusion in either MG0004 or the feeder study MG0003. Specifically, baseline for ADA is defined as:

- MG0003 ADA baseline if participants randomized to RLZ groups in MG0003 (note: MG0003 post-baseline ADA samples will not be considered for the ADA participant status in MG0004);
- MG0004 ADA baseline if participants randomized to placebo in MG0003.

If the ADA sample status for the visit prior to the first dose of RLZ is missing, the last non-missing sample will be used.

ADA/NAb Participant Status

The ADA participant status will be classified on study participant and group level as outlined below (Shankar et al. 2014; Rup et al, 2015). A description of how study participants will be categorized for the immunogenicity assessment is provided in

Table 10-1.

Individual study participants will be assessed for ADA participant status, composed of 6 categories: ADA negative, inconclusive, and ADA positive, whereby a positive participant’s status is determined as originating from a treatment-induced, boosted, reduced or unaffected ADA response.

Study participants who are identified as being treatment-induced or treatment-boosted ADA-positive will be grouped as treatment-emergent (TE)-ADA positive participants. Study participants who are identified as being treatment-reduced or treatment-unaffected ADA-positive will be grouped as non-TE-ADA positive participants. Both TE-ADA positive and non-TE-ADA positive participants will be further classified as NAb negative or NAb positive.

The individual and combined ADA participant categories will be derived and summarized through each of the scheduled sampling points (ie Week 5, 9, 21, 33, 45, 52 and 60) and EOS visit, unless specified otherwise.

Table 10-1: Terms and Definitions for ADA Status Evaluation in Study Participant

Classification	Classification Label	Definition
Individual participant categories		
1	Pre-ADA negative – treatment induced ADA negative (ADA-NEG)	Study participants who have an ADA negative sample at Baseline and at all sampling points post-Baseline up to the timepoint of interest.
2	Inconclusive	Study participants who have an ADA positive or negative Baseline sample and some post-Baseline samples are missing or inconclusive, while other post-Baseline samples are ADA negative up to the timepoint of interest.
3	Pre-ADA negative – treatment induced ADA positive (TI-POS)	Study participants who have an ADA negative sample at Baseline and have at least one ADA positive sample at any sampling point post-Baseline up to the timepoint of interest.
4	Pre-ADA positive – treatment boosted ADA positive (TB-POS)	Study participants who have an ADA positive sample at Baseline and at least one ADA positive sample at any sampling point post-Baseline up to the timepoint of interest, with increased titer values compared to Baseline (greater than a predefined fold difference increase from Baseline value which will be defined within the validation of the assay i.e. MSR of the assay).

5	Pre-ADA positive – treatment reduced ADA positive (TR-POS)	Study participants with an ADA positive sample at Baseline, and ADA negative samples at all sampling points post-Baseline up to the timepoint of interest.
6	Pre-ADA positive – treatment unaffected ADA positive (TU-POS)	Study participants with an ADA positive sample at Baseline and an ADA positive sample at any sampling point post-Baseline up to the timepoint of interest, with titer values of the same magnitude as Baseline (less than a predefined fold difference from the Baseline value which will be defined within the validation of the assay, i.e. MSR of the assay ¹).
Combined participant categories		
7	Treatment emergent ADA positive (TE-POS)	Includes study participants who are treatment induced ADA positive (category 3) or treatment boosted ADA positive (category 4).
8	Non-treatment emergent ADA positive (Non-TE-POS)	Includes study participants who are treatment reduced ADA positive (category 5) or treatment unaffected ADA positive (category 6).
9	Treatment emergent ADA positive – NAb positive (TE-POS, NAb-POS)	Includes study participants who are treatment emergent positive (category 7) and have at least one NAb positive sample.
10	Treatment emergent ADA positive – NAb negative (TE-POS, NAb-NEG)	Includes study participants who are treatment emergent positive (category 7) and have no NAb positive samples.
11	Non-treatment emergent ADA positive - NAb positive (Non-TE-POS, NAb-POS)	Includes study participants who are non-treatment emergent positive (category 8) and have at least one NAb positive sample.
12	Non-treatment emergent ADA positive - NAb negative (Non-TE-POS, NAb-NEG)	Includes study participants who are non-treatment emergent positive (category 8) and have no NAb positive samples.
¹ The fold difference increase from baseline value, i.e. the minimum significant ratio (MSR=1.36) determined during assay validation, will be reported in the relevant tables, listings and figures. It reflects the fold difference in titer level that considered higher than the assay variation in titer determination.		

